PROTOCOL SYNOPSIS

TITLE OF CLINICAL TRIAL:

Phase 3 double-blind placebo-controlled efficacy trial of EVO100 vaginal gel for the prevention of urogenital *Chlamydia trachomatis* and *Neisseria gonorrhoea* infection

INVESTIGATIONAL PRODUCT(S):

After a screening period of up to 35 days, women will be randomized to receive either EVO100 or placebo:

EVO100 vaginal gel (previously known as Amphora) is supplied in individually wrapped 5 g single-dose, pre-filled vaginal applicators. EVO100 is a viscous, off white to tan gel of uniform consistency. Its active ingredients are lactic acid United States Pharmacopeia (USP), citric acid USP, and potassium bitartrate USP.

Universal placebo gel (UPG) is an isotonic non-buffering gel, containing 2.7% hydroxyethylcellulose, sorbic acid, sodium hydroxide, sodium chloride, and purified water and supplied in individually wrapped 5 g single-dose, pre-filled vaginal applicators.

CLINICAL PHASE: Phase 3

CLINICAL TRIAL OBJECTIVES:

Primary Objective:

- To evaluate the efficacy of EVO100 vaginal gel in the prevention of urogenital *Chlamydia trachomatis* (CT) and *Neisseria gonorrhoea* (GC) infection

Secondary Objectives:

- To assess impact of EVO100 vaginal gel on overall sexual satisfaction and overall product satisfaction over the course of the clinical study
- To evaluate the safety of EVO100

Exploratory Objectives:

- To determine the impact of EVO100 vaginal gel use rate (subject adherence to instructed use) on the efficacy in the combined infections
- To assess other subject satisfaction with EVO100 vaginal gel over the course of the clinical study

OUTCOME MEASURES:

Primary:

- A composite endpoint, defined as a comparison between the proportion of subjects who are defined study successes vs study failures among the intervention groups (EVO100 or placebo) with success defined as subjects completing the trial to Visit 5 without any CT or GC infection.

Secondary:

The secondary outcomes for this study will be assessing the following proportion of subjects:

- with overall sexual satisfaction using the female sexual function index (FSFI) overall sexual

satisfaction question at Visit 5 and not having a CT or GC infection
 
with overall sexual satisfaction using the FSFI overall sexual satisfaction question at visit 5reporting overall product satisfaction at Visit 5Incidence of adverse events (AEs) (descriptive analysis)

Exploratory:
 
Exploratory assessments include:
 
Comparison of compliance with EVO100 vaginal gel usage vs placebo usage during study (rate of product use adherence vs placebo)Subgroup analyses of the primary endpoint (the proportion of subjects who are deemed success vs failure) will be performed for the following:
Subjects with 0%, >0% and <20%, ≥20%, ≥40%, ≥60%, ≥80% and 100% product use adherenceDescriptive analysis of failure components defined as failures for the primary endpointComparison of PROMIS SexFS Satisfaction, Pain and Lubrication subscales with EVO100 vaginal gel usage vs placeboComparison of FSFI Lubrication and Pain subscales with EVO100 vaginal gel usage vs placeboComparison of Patient Global Impression of Change (PGIC) with EVO100 vaginal gel usage vs placebo

CLINICAL TRIAL DESIGN:
 
This is a Phase 3, double-blind, placebo-controlled study in approximately 90 sites in the United States (US) and European Union (EU) over approximately 16 weeks of use in women age ≥13 years who are at risk of urogenital CT or GC infection.

TREATMENT DURATION:
 
After a screening period of up to 35 days, women will be randomized to receive either EVO100 or placebo. Each woman will participate in the study until she has completed 16 weeks of treatment or observation or tests positive for CT or GC infection. This will include women who discontinue treatment but continue other study assessments to Visit 5. The intervention period is defined as Visits 1 to 5. There will be a follow-up visit (Visit 6) 4 weeks after the last intervention visit. Visits 5 and 6 will be combined for subjects who discontinue the study early. These periods are outlined in the Schedule of Assessments (Table 1). The protocol-defined period of observation is 20 weeks.

SAMPLE SIZE:
 
Assuming a two-sided alpha of 0.05, the failure rate for control subjects to be 32.5%, and the failure rate for the treatment subjects to be 25.5%, a sample of 881 subjects per treatment arm is needed (1762 subjects overall) to achieve 90% power. Anticipating approximately 5% of subjects will have non-negative CT/GC results in enrollment based on the Phase 2B/3 study data, this yields a sample size of 1856 women.

ANALYSIS POPULATION:

This study will utilize three analysis populations: Intention-to-treat (ITT), modified Intention-to-treat (mITT), and safety. The ITT population will consist of all randomized subjects. The mITT population will be the analysis population for the primary endpoint and will consist of all randomized subjects who are negative for chlamydia and gonorrhea at enrollment and are provided with study product. Lastly, the safety population will be based on subjects with documented use of any study product. Analyses using the ITT and mITT populations will be performed based on the treatment randomized. Meanwhile, safety analyses will be based on the treatment received.

STUDY POPULATION:

Study Sites:

The study will be conducted at up to 90 clinical sites in the US and/or EU. Subjects will be selected for the study according to the eligibility criteria detailed below.

Inclusion Criteria:

1. Subjects must meet both of the following criteria:
 - a. Healthy female subjects at least 13 years of age with a urogenital CT and/or GC infection (documented in a retrievable medical record) within the 16 weeks prior to enrollment and one or more of the additional risk factors included in point ii below:
 - i. Acceptable documentation will include:
 1. Laboratory report(s) confirming CT and/or GC infection
 2. Copy of clinic note from the date of diagnosis confirming CT and/or GC infection and indicating the date of diagnosis and/or date of treatment
 3. Evidence of dispensed medication (from pharmacy records or clinic notes) for antibiotic therapy used for treatment of CT and/or GC
 - ii. PLUS one or more of the following additional risk factor(s):
 1. 13 to 24 years of age at the screening visit
 2. New sex partner within the past 12 weeks (84 days)
 3. More than one current sex partner
 4. Knowledge that current sex partner has multiple partners
 5. Partner with known sexually transmitted infection (STI)
 6. Inconsistent condom use among persons who are not in a mutually monogamous relationship
 - b. If medical record of previous infection cannot be obtained within two weeks of screening date, following three documented attempts to obtain the medical records, subjects may be enrolled only if they have two or more of the following risk factors, in addition to self-reported history of infection within 16 weeks prior to enrollment:
 - i. 13 to 24 years of age at the screening visit
 - ii. New sex partner within the past 12 weeks (84 days)
 - iii. More than one current sex partner
 - iv. Knowledge that current sex partner has multiple partners
 - v. Partner with known STI
 - vi. Inconsistent condom use among persons who are not in a mutually monogamous relationship

[figure not shown]

2. Ability to understand the consent process and procedures. For minors, the ability to obtain consent from parents/legal guardian and assent by minor subjects as applicable according to local regulations.3. Agree to be available for all study visits including Visit 5 and follow-up Visit 6 and comply with follow-up on staff appointment reminders4. Negative pregnancy test5. Negative CT and GC nucleic acid amplification test (NAAT) at screening or positive CT or GC NAAT and receives standard of care (SOC according to CDC or World Health Organization [WHO] guidelines) treatment prior to enrollment with subsequent negative CT and GC NAAT testing at enrollment visit6. Agree to use a woman-controlled method of contraception that is not directly delivered to the vaginal mucosa (with the exception of a vaginal ring) throughout the duration of the study, such as oral contraceptives, birth control implants, intrauterine devices (IUDs), or tubal ligation. Condom use only is not an acceptable form of contraception for this study7. Able and willing to comply with all study procedures, including the use of eDiaries and reporting of all Adverse Events and concomitant medications.8. Reports vaginal sexual intercourse with a male partner at least three times per month in the previous month and anticipates vaginal sexual intercourse regularly for the duration of the study9. Agree to abstain from douching or any form of vaginal suppository use (other than investigational product) during course of study

Exclusion Criteria:


1. Participation in any study with an investigational compound or device within 30 days prior to signing informed consent.2. Used Phexxi (lactic acid, citric acid, and potassium bitartrate) as a contraceptive vaginal gel within 7 days prior to enrollment (may be enrolled at a later date if all other criteria are met).3. In the opinion of the Investigator, has a history of substance or alcohol abuse in the last 12 months4. In the opinion of the Investigator, has issues, conditions, or concerns that may compromise the safety of the subject, impact the subject's compliance with the protocol requirements, or confound the reliability of the data acquired5. Is a close relative of or is an Evofem, approved contract research organization (CRO), ICON, or clinical site employee regardless of direct involvement in research activities6. Pregnant (or actively trying to become pregnant) or breastfeeding7. Women who have undergone a total hysterectomy (had uterus and cervix removed). However, women with subtotal hysterectomy with an intact cervix may be enrolled8. Inability to provide informed consent or assent9. Has a history or expectation of noncompliance with medications or intervention protocol10. Has engaged in sexual vaginal intercourse or douching, or used of any form of vaginal suppository or intravaginal device (with the exception of contraceptive vaginal ring or tampons) for 24 hours prior to enrollment (may be enrolled at a later date if all other criteria are met)

11. Menstruating at enrollment (may be enrolled at a later date if all other criteria are met)
12. Is currently being treated, or has been treated, for a period of 21 days prior to enrollment, with any antibiotics. Note: Subjects will not be discontinued from study treatment post-randomization if treated with antibiotics for an infection other than CT or GC.
13. In the opinion of the Investigator, has signs/symptoms that indicate persistence of CT or GC infection diagnosed at screening, new interval infection, and/or a failure to comply with or complete the prescribed treatment regimen following a positive screening NAAT
14. Women who regularly use douches, vaginal medications, vaginal products, or suppositories who do not agree to stop these products for the duration of the study
15. Women who are currently using contraceptive products that are directly delivered to the vaginal mucosa (with the exception of contraceptive vaginal ring), such as diaphragms, spermicides, or any vaginally applied or inserted products containing nonoxynol-9 (N-9) or Phexxi (lactic acid, citric acid and potassium bitartrate)
16. Vulnerable populations, including children <13 years of age, pregnant women, prisoners, institutionalized persons, persons without decisional capacity, persons without phone and/or without domicile (homeless).

Figure 1 Schematic Flow of Study Design

Abbreviations: CT = *Chlamydia trachomatis*, GC = *Neisseria gonorrhoea*, NAAT = nucleic acid amplification test

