3 STUDY DESIGN

3.1 General Study Design

At total of 1730 women, ages ≥ 18 , who had a documented urogenital CT or GC infection or an undocumented self-reported CT or GC infection with risk factors, at any time over the 17 weeks preceding the enrollment visit, or positive at screening visit will be enrolled. A high prevalence of CT infection has been observed in those who were treated for urogenital chlamydial infection during the preceding several months. The second infection may result from infection through an untreated partner or exposure through a new partner. By including only women who have had a CT or GC infection within the past 17 weeks, this study targets those at high risk for infection.

At screening, subjects will be tested for a current GC/CT infection by nucleic acid amplification test (NAAT) via vaginal swab. Those negative for current infection will be enrolled. Those who test positive for CT/GC infection at screening will receive standard of care treatment. To meet eligibility criteria, these subjects will not be enrolled until 3 to 4 weeks after screening (at least 21 days after treatment).

[figure not shown]
Eligible participants will be enrolled and randomized 1:1 (865 subjects per treatment arm) to either EVO100 Gel, 5g or HEC placebo 5 g supplied in a pre-filled, single-dose applicator. A baseline vaginal pH and a full gynecologic examination (including bimanual and speculum) will be obtained at enrollment.

Subjects are instructed to apply EVO100 or placebo gel immediately before or up to one hour prior to coitus for the duration of the 16-week intervention period. EVO100 or placebo is to be re-applied in the same manner for each occurrence of sexual intercourse. Subjects will keep an electronic diary (eDiary) to document sexual activity and product use.

Every 4 weeks (5 visits), all subjects will return to the clinic for repeat CT/GC NAAT (vaginal swab), urine pregnancy (urinary β -human chorionic gonadotrophin [uHCG]) testing, eDiary review, and return of unused investigational product. At Visits 2 to 4, subjects will be re-supplied with EVO100 or placebo gel. At Visit 5, subjects will return unused investigational product and continue to use their eDiaries but will not be resupplied with EVO100 or placebo gel.

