Subjects will return for a follow-up visit 4 weeks after the intervention period or after their last dose of study medication. At this time, CT/GC NAAT (vaginal swab), pregnancy (uHCG) testing, gynecological exam, and eDiary review will be performed.

Figure 1 Schematic Flow of Study Design

Abbreviations: CT = *Chlamydia trachomatis*, GC = *Neisseria gonorrhoeae*, NAAT = nucleic acid amplification test

⁽¹⁾In the event a subject has CT or GC infection diagnosed at a local healthcare facility during the period between visits, the infection and treatment will be documented and every effort to obtain a medical record will be made.

Screening and Eligibility

Subjects who consent may be screened if they have a known case of CT or GC within 17 weeks of enrollment, or suspicion of current CT or GC infection (subsequently confirmed with NAAT test at Screening Visit). Subjects randomized within 35 days of initial screening do not need to be re-screened.

Intervention and Follow-up Period

The intervention period is defined as Visits 1 to 5. There will be one follow-up visit (Visit 6), 4 weeks after the last intervention visit or last dose of study product. These periods are outlined in the schedule of assessments (Table 2). The protocol-defined period of observation is 20 weeks. In the event a subject has CT or GC infection diagnosed at a local healthcare facility during the period between visits, the infection and treatment will be documented and every effort to obtain a medical record will be made. These subjects will be considered as failures.

Safety Follow-up After Protocol-defined Period of Observation

This period includes safety follow-up as required by Good Clinical Practice (GCP) and standard clinical study practice. Adverse events determined to be at least possibly related to the

investigational product continuing after the final study visit (Visit 6) will be followed until resolution or stable status as determined by the Investigator.

Study Conduct Strategies due to Coronavirus Disease -2019

Based on the US Food and Drug Administration (FDA) guidance, Coronavirus disease 2019 (COVID-19) strategies are planned for this study to ensure adherence to best practices for study conduct.

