AE Assessment	X	X	X	X	X	X	X
Medical/Sexual History	X	X	X	X	X	X	X
Last Menstrual Period	X	X	X	X	X	X	X
Physical Exam		X					
Targeted Physical Exam ⁽⁶⁾			X	X	X	X	X
Body Weight/Height		X					
Vital Signs		X					
Gynecologic Exam		X				X ⁷	X ⁷
Urine HCG	X	X	X	X	X	X	X
Vaginal pH		X					
Self-collected CT/GC NAAT			X	X	X	X	X
Clinician-collected CT/GC NAAT	X	X					
eDiary Setup		X					
eDiary Review			X	X	X	X	X
Female Sexual Function Index (FSFI)	X	X	X	X	X	X	X
PROMIS Sexual FS (PROMIS® Brief Profile Sexual Function and Satisfaction)	X	X				X	X
Subject Sexual Impact Questionnaire			X	X	X	X	X
Product Satisfaction Questionnaire			X	X	X	X	X

Patient Global Impression of Change (PGIC)		X				X	X
Return Unused Study Product			X	X	X	X	

Abbreviations: AE = adverse event, CT = *Chlamydia trachomatis*, eDiary = electronic diary, GC = *Neisseria gonorrhoeae*, HCG = human chorionic gonadotropin, HIPAA = Health Insurance Portability and Accountability Act, NAAT = nucleic acid amplification test; V = study visit.

⁽¹⁾ The intervention period is defined as Visits 1 to 5. In the event a subject has CT or GC infection diagnosed at a local healthcare facility during the period between visits, the infection and treatment will be documented and every effort to obtain a medical record will be made.

⁽²⁾ Screening period may be up to 35 days. If subjects NAAT results are positive, they will be first treated by SOC then will return 3-4 weeks after Screening Visit (at least 21 days after treatment) for Enrollment/Visit 1. If the screening period extends past 35 days, subjects will not be enrolled and will need to be rescreened.

⁽³⁾ Subjects must be asked to abstain from vaginal intercourse in the 24 hours preceding Study Visits 2 through 5.

⁽⁴⁾ Subjects will be asked to return \pm 7 days within each visit window.

⁽⁵⁾ The procedures for Visit 5 should be followed for the Early Termination Visit.

⁽⁶⁾ For unscheduled visits: includes provision to contact subjects or allow unscheduled visits for managing AEs.

⁽⁷⁾ The gynecologic examination will be conducted during unscheduled visits, as necessary and during end of study and end of treatment visits. The gynecologic examination will not be conducted if the end of study/end of treatment visit is remote due to COVID-19.

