4 STUDY ENDPOINTS

4.1 Primary Endpoint

- The primary efficacy endpoint is the proportion of subjects who are defined as study successes versus study failures among the intervention groups (EVO100 or placebo).
Estimand Framework
 - FDA Submission
 - Success is defined as subjects completing the trial to Visit 5 without any of the following: CT/GC infection, usage of prohibited antibiotics during the study, an invalid CT/GC test at Visit 5.
 - The mITT population will be used, and the Chi-Square test will be used to compare the failure rates in EVO100 and placebo.
 - EMA Submission
 - The parallel primary efficacy endpoints define success through Visit 5 as:
 - CT Infection Endpoint:
 - The proportion of subjects without a CT infection, CT prohibited antibiotics, or invalid Visit 5 CT test.
 - GC Infection Endpoint
 - The proportion of subjects without a GC infection, GC prohibited antibiotics, or invalid Visit 5 GC test.
 - The mITT population will be used and the Chi-Square test will be used to compare the failure rates in EVO100 and placebo.

Note: These two parallel primary endpoints enable efficacy to be assessed separately for CT and GC. In this way, if the study is successful for either CT or GC but not for both, an indication for prevention of just one of the two pathogens could still be granted. Both primary endpoints will be tested at the 0.05 significance level (with no adjustments for multiplicity of statistical testing).

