9 CHANGES TO PLANNED ANALYSIS FROM STUDY PROTOCOL

The following changes to the analysis plan have changed since the approval of the protocol:

- 1) Male condom usage summary statistics.
- 2) Assessing the effect of male condom usage on study success rates.
- 3) Added sensitivity analysis for the primary endpoint to check the impact of the use of prohibited medication.
- 4) Patients with duplicate enrollments will have their second entries will be excluded from all analyses
- 5) Added secondary analyses for separate CT and GC Only analyses. These analyses will serve as parallel primary endpoints for the EMA marketing authorization application.
- 6) An exploratory analysis of the FDA primary endpoint by subgroups of prior infection documentation status (available, not available)
- 7) A subgroup analysis of the FDA primary endpoint by Age groups (18-24, 25-45, 46-64, 65+)

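### The protocol synopsis stops follow-up at the first CT or GC positive while the SAP tests everyone every 4 weeks; if the stop applies, the separate CT and GC endpoints score untested time as negative

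*Protocol*

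**What the plan says.** - **Protocol synopsis, Treatment Duration.** A woman takes part "until she has completed 16 weeks of treatment or observation or tests positive for CT or GC infection". The next sentence reads "This will include women who discontinue treatment but continue other study assessments to Visit 5", without saying whether women with a positive test are among them. Then: "Visits 5 and 6 will be combined for subjects who discontinue the study early".
- **SAP section 3.1.** "Every 4 weeks (5 visits), all subjects will return to the clinic for repeat CT/GC NAAT (vaginal swab"). No stop at a first positive is stated here or in the schedule of assessments (Table 2). Also: "Subjects will return for a follow-up visit 4 weeks after the intervention period or after their last dose of study medication", with a CT/GC NAAT at that visit.
- **SAP section 3.3, Table 2 footnote.** "The procedures for Visit 5 should be followed for the Early Termination Visit". Visit 5 includes the CT/GC NAAT.
- **SAP section 4.1, EMA.** "These two parallel primary endpoints enable efficacy to be assessed separately for CT and GC". Section 4.2 makes the same two endpoints FDA secondaries. Section 9 lists them as added after the protocol: "These analyses will serve as parallel primary endpoints for the EMA marketing authorization application".
- **SAP sections 7.2.1 and 8.6.2, separate endpoints.** A woman whose status is not known through Visit 5 (at least day 105) is taken as uninfected. Every mITT woman is in the denominator. A woman who takes a drug prohibited for one pathogen fails that pathogen's endpoint. No drug lists appear in the supplied text.

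**The concern.** Stopping at the first positive suits the protocol's composite, because the first infection of either kind settles it. It does not suit two separate endpoints. A woman who is CT-positive at Visit 2 (week 4) would have 12 of the 16 weeks without scheduled GC tests, yet would count as a GC success unless GC was found by another route or she took a GC-prohibited drug.

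This differs from ordinary dropout. Measurement is stopped by the plan, and the trigger is the other parallel primary, which the gel is meant to change. The arm with more CT infections loses more GC observation. Neither document says how one pathogen is scored after a positive for the other. The one sensitivity analysis in SAP section 8.6.2 removes the antibiotic criterion from the FDA composite and does not touch this.

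What is at stake is the purpose given in SAP section 4.1, that one pathogen's indication could rest on its own endpoint. The rarer pathogen loses most.

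**Working it through.** **1. The plan's own figure.** With p the mean of p1 and p2, power = Φ{[|p1−p2| − 1.96·√(2p(1−p)/n)] / √([p1(1−p1)+p2(1−p2)]/n)}. For the composite in SAP section 5 (37.5% vs 30.5%, n = 821): (0.07 − 1.96×0.02338)/0.02332 = 1.037, so power is 85.0%, as stated. A first positive is already a composite failure, so this figure is not affected. The documents give no rate or power for CT or GC alone.

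**2. Assumed inputs (not in the documents).** 16-week risks: CT 20% placebo, 13% EVO100; GC 6% placebo, 3% EVO100. There are 821 women per arm, constant hazards, and tests at weeks 4, 8, 12 and 16. No later test counts, and no prohibited drug is triggered. With full observation, GC power is Φ[(0.03 − 1.96×0.01023)/0.01021] = 83.5%.

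**3. Stop rule, independent risks.** Let g and c be the probabilities of staying GC-free and CT-free over 4 weeks. GC is seen in interval j only if CT was absent in all earlier intervals, so observed GC = Σ (1−g)·(gc)^(j−1), j = 1 to 4.
- Placebo: g = 0.94^¼ = 0.98465, c = 0.80^¼ = 0.94574. The terms 1.535 + 1.429 + 1.331 + 1.240 sum to 5.54%.
- EVO100: g = 0.97^¼ = 0.99241, c = 0.87^¼ = 0.96578. The terms 0.759 + 0.727 + 0.697 + 0.668 sum to 2.85%.
- The difference falls from 3.0 to 2.7 points and power to 77.5%.

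**4. Stop rule, shared risk.** Multiply both hazards by a gamma frailty with mean 1 and variance 1.5 (an assumption), so L(s) = (1+1.5s)^(−1/1.5). With 4-week rates a for CT and b for GC set to give the same 16-week risks, observed GC = Σ {L[(j−1)(a+b)] − L[(j−1)a + jb]}.
- Placebo (a = 0.0663, b = 0.0162): 4.95%. EVO100 (a = 0.0387, b = 0.0078): 2.65%.
- The difference is 2.3 points and power 68.5%.

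**5. One later NAAT that counts, 4 weeks after the positive.** Replace the (j−1) on the CT term by max(j−2, 0). Power is 80.6% (independent) or 76.5% (shared risk), so about half the loss returns.

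**6. No true GC effect (6% in both arms, CT as above).** Observed GC is 5.54% placebo vs 5.70% EVO100 (independent), or 4.95% vs 5.32% (shared risk): 0.2 to 0.4 points against EVO100.

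**7. Range.** A second model used placebo CT 10-25% and GC 4-10%, risk ratio 0.81 or 0.50, and risks independent or with 30% of women at four times the hazard.

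| Share of true cases missed | Placebo | EVO100 |
|---|---|---|
| GC endpoint | 3.8-14.5% | 1.9-11.8% |
| CT endpoint | 1.5-4.9% | 0.7-4.2% |

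In every scenario placebo loses the larger share.

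**8. If treatment of CT is prohibited under the GC endpoint.** Suppose every CT-positive woman takes such a drug and risks are independent. Then GC failure is 1 − 0.80×0.94 = 24.8% on placebo. With no GC effect it is 1 − 0.87×0.94 = 18.2% on EVO100. The bias reverses: GC is overcounted, and the CT effect appears as a GC effect.

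**9. What continued sampling recovers.** Assume that product stops at the CT positive and that EVO100 women then carry the placebo GC rate. With sampling to Visit 5, GC is 6.0% vs 3.15% (independent; power 78.9%) or 6.0% vs 3.36% (shared risk; power 71.8%). With no true GC effect both arms show 6.0%, so the artefact in step 6 disappears.

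**The case against.** A reader might infer that nothing measures GC after a CT positive. The documents do not support that. The NAAT covers both pathogens, so co-infection at the positive visit is seen. The combined Visit 5/6, the early-termination procedures and the SAP follow-up visit may each supply a later NAAT. SAP section 3.1 also counts infections diagnosed locally between visits as failures. What is not said is whether a closing NAAT counts as a result through Visit 5.

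A reader might also infer that the stop rule is certainly in force and that the schedule was never adapted. That is not shown. SAP section 3.1 has everyone tested every 4 weeks, and the synopsis allows assessments to continue after treatment stops. The SAP serves protocol Version 4.0, and the supplied synopsis differs from the SAP (age 13 vs 18, infection within 16 vs 17 weeks, 1856 vs 1730 women), so it may be another version. The protocol's own schedule table and the flow figure are not in the supplied text.

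Three further points stand. The direction depends on drug lists that we cannot see. The sizes rest on assumed rates, and the largest loss on one assumed frailty variance. Where undercounting applies, it usually works against EVO100 and does not create false efficacy.

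The conflict between the two texts and the missing scoring rule remain.

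**Conclusion.** The point holds as an inconsistency with a conditional bias. The synopsis and SAP section 3.1 cannot both describe follow-up after a first positive, and the SAP has no rule for the second pathogen. If the stop rule applies, untested time is scored as negative in the EMA parallel primaries and the FDA secondaries. Unless treatment of the first infection is prohibited under the other endpoint, the second pathogen is undercounted, more so in the arm with more first infections.

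Under the assumed rates GC power falls from about 84% to 78% (independent risks) or to 68-69% (shared risk), and about half of the loss is recovered if one later NAAT counts. The true size cannot be derived from the documents. The CT endpoint is less affected if CT is the commoner infection, as assumed. The FDA composite is not affected.

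It should not be inferred that continued sampling restores full power. It removes the measurement bias, but if product has stopped it moves power only from 77.5% to 78.9%, or from 68.5% to 71.8%.

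**What to change.** Confirm the rule in protocol Version 4.0, then:

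1. Reconcile the synopsis (Treatment Duration) with SAP section 3.1 so that the already scheduled CT/GC self-swab continues to Visit 5 after a first positive, and score each pathogen on its own results. This concerns sampling only and changes neither product use nor treatment. State that it removes the measurement bias but recovers only part of the power if product has stopped. Also state whether a closing NAAT counts through Visit 5.
2. If sampling cannot continue, add beside the chi-square, for both EMA endpoints, a cause-specific analysis by visit interval in which women contribute only tested intervals. State its limit. In the model above it returns 6.0% vs 3.0% for GC if risks are independent, but about 5.3% vs 2.8% under the shared-risk frailty, so only part of the bias goes.
3. State how treatment for one pathogen is scored in the other pathogen's endpoint, and point to the drug lists.

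Cost: protocol and SAP wording, plus at most three further scheduled swabs (Visits 3 to 5) for a woman first positive at Visit 2; or, without continued sampling, one added analysis.
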